# Site selection and delivery

The study will be delivered through a select network of NHS Trust sites. The study will start with six trusts over a 4-6 month period to ensure the design of the study is working as expected before it is expanded to the number of trusts required to deliver the full sampling size. Provisional modelling has suggested that this could be up to 25-40 trusts but part of the initial implementation will involve monitoring of the consent and sample rates to identify the final number required.

Our site selection aims to ensure successful delivery of the study with a particular emphasis on ensuring diversity of participation. Criteria to determine which sites to approach to be part of the first six centered on:

- High birth volumes
- High percentage of births in hospital setting
- Level of diversity of patient reported ethnicity compared to national average
- Level of socio-economic deprivation compared to national average
- Previous engagement in the 100,000 Genomes Project, other national genomics research or the Baby and Mum Sample Study
- Track record of maternity research
- Nature of population served urban vs rural
- Support of Trust leadership to participate in the study factoring in capacity of maternity service to support recruitment

[figure not shown]
These criteria will be used to identify trusts to participate in the further implementation and scale up but a critical factor will also be ensuring we are gathering evidence in different types of trusts e.g. rural vs city, less genomically aware trusts etc.

Potential participating trusts will be approached consecutively, and invited to take part in the study. Diversity within the sample will be promoted through careful site selection, and aiming for a broadly representative sample of babies born in the country.

# End-to-end participant experience

In the following sections, the different elements of delivery of the programme are described. The end-to-end experience form the participants' perspective is shown in Figure 6.

Figure 6 - Participant experience

# 7. Recruitment and Consent

#### Introduction

Genomic medicine and research presents important and practical challenges which require careful ethical consideration. These include the complexity and uncertainty of genomic information, implications for the wider family, and the link between research and clinical practice. 157, 158 The study will follow established legal and regulatory standards for seeking informed consent of its participants, or those who would consent on their behalf, in this case, someone with legal parental responsibility providing consent on behalf of the newborn. 159,160

Parents who consent to the Generation Study on behalf of their child would agree to participation in the screening and evaluation aspects of the study (this Protocol), and to participation in the National Genomic Research Library (the NGRL Governance Framework) for ongoing data linkage and wider research.

In conventional terms, as was the case with the 100,000 Genomes Project and National Genomic Research Library, a 'broad' consent model is proposed whereby permission is given for future research. The exact nature of this future research may as yet be unknown; however, it will fall within the boundaries of acceptable uses as outlined in the National Genomic Research Library protocol. Further detail about the model of consent for this study and it's ethical underpinnings can be found in Section 17 (Regulation, Ethics and Legal Considerations).

# The process of recruitment and consent

Recruitment may take place across a number of settings. Whilst the mainstay of recruitment is study hospitals, mothers/birthing parents may also be approached to participate at smaller antenatal clinics. It is critical that these clinics routinely provide standard NHS care for the recruiting Trust. Study-trained Trust research staff should still perform the consent activities at any outsourced clinic via the research team and trained clinical healthcare professionals at each study site. Samples should still be procured according to the samples collection procedures detailed in Section 8.

The process for recruitment aims to maximise time and opportunities for parents to make an informed decision about their child taking part in the study during pregnancy, given the need to collect, sequence and analyse samples in a timely manner after birth. The exact process may vary in each study site; a general overview of the recruitment and consent process can be found in Figure 7. Further information about how public, patient and professional insights have shaped the recruitment and consent process can be found in Section 4 (Stimulus and development of this programme).

[figure not shown]

Figure 7 - The process of recruitment and consent

**Passive awareness:** parents may learn about the study by viewing study materials (e.g., seeing a poster or leaflet, viewing the microsite, or receiving social media communications about the study), through word of mouth or community-specific initiatives led by site study teams. If they are interested in taking part, they will be directed to speak to their study team who can support them with decision making and recording consent. In some cases, potential participants may find out about the study if they are sent a text message using Generation Study wording, or they may see notifications on maternity groups like Badger net.

- Initial approach: a member of the site study team may pro-actively approach parents from around 20 weeks' gestation to invite them to participate in the study. This may include when they are attending their 20-week anomaly scan appointment where an approach may be made in the scan waiting room. Site study teams will be aware of study exclusion criteria to minimise approaching parents who would not be eligible to take part. Parents will be given a copy of the study leaflet or patient information sheet (depending on the amount of time available to have an initial discussion about the study), and signposted to the study microsite/digital information sheet. Parents will be asked for permission to be contacted by the site study team to further discuss participation. It should be noted that in some cases potential participants may be approached at a later stage in pregnancy, and in other those in early pregnancy who have heard about the study and expressed interest in participating may provide consent.
- Time to consider: parents will be given time to consider participation in the study by reviewing hard-copy and digital resources (see section below), and to ask any questions they have about the study by speaking with a member of their study team. Parents may decide to take part on the same day when they are initially approached about the study, or may want more time to consider. Participant materials and study teams will highlight the importance of discussing participation with others with parental responsibility such as the baby's other parent (where available), as well as family members or other individuals helping to make decisions about their baby. Although only one person with legal parental responsibility would consent to their baby taking part in the study, where parents have different opinions about agreeing to take part, it will be recommended that they do not participate. This is to

emphasise the importance that both parents have a say in the interests of familial decision-making and in the context of genomics. Drop-in information sessions (run face to face or virtually at site or national level) may also be used to provide further information about the study.

- **Decision making:** prior to delivery, parents will be contacted by the site study team (including by telephone or face to face at hospital appointments) to confirm eligibility, ensure provision of information about the study and answer any questions. More than one conversation may take place, depending on individual parent needs. Some potential participants may be approach in induction of labour wards or in late pregnancy. A specific pathway has been developed to facilitate this detailed at the end of this section.
- Recording consent: if and when the parent agrees to take part in the study, they will review the study consent form with a member of the site study team and their consent decision will be recorded in a secure data capture system along with demographic information. Consent may be recorded in a face to face consultation, or through verbal agreement following a telephone or video consultation. The method of recording consent will depend on processes at the study site, and availability and convenience to the parent. Study staff will confirm the identity of the individual they are speaking to, including name, date of birth and relationship to the unborn child. Once consent has been received, parents will be informed that they will receive a record of their consent along with a letter welcoming them to the study, either by email following the telephone or video consultation, or in hard copy following a face to face appointment. A copy will also be included in the mother / birthing parent's hospital patient record. The duration of storage of these records will be at the discretion of each Trust, and will exceed five years, in line with Good Clinical Practice expectations.
- Registration and data collection: participants will be enrolled by the site study team using a Genomics England-provided web-based application. The application will also be used for registering sample details post birth. The users of the application will be authenticated via systems conforming to standards expected for the data held in the system (e.g., NHS Care Identity Service 2 and Role Based Access Control applied). The data collected during enrolment will be limited to that required for capturing consent, demographic details, number of expected babies and language requirements to facilitate return of results. To ensure consistency with NHS data, the application will query the Personal Demographics Service (PDS) Spine when collecting demographic data on the participant. Demographic data on the babies after birth will be received via NEMS notifications and stored in the application.
- **Sample collection:** at the time of sample collection on the day that the baby is born, site study teams will allow time for any further questions and obtain consent to take the study samples, ensuring parents are aware of the opportunity to withdraw from the study.

If parents have questions through the course of reviewing information about the study, they will be given the contact information of the team delivering the study at their hospital. They will also be able to contact Genomics England directly via the Genomics England service desk.

Each point of contact with parents throughout the process of recruitment (e.g., initial invitation to the study, conversations about participation) will be documented locally in hospital site records. Where it is not appropriate to offer the study to parents because they meet one or more exclusion criteria, this will also be recorded at site level.

Some parents may be approached at different points in time - for example, if an anomaly was found on the 20-week scan and parents are in distress, such that it was not appropriate to discuss a research study. In these instances, the site study team will use their expert judgement, and liaise with other clinical colleagues as appropriate, on the suitable timing for asking parents to take part. In all cases, recruitment would only take place where parents can be given time to fully consider their participation and make an informed decision.

Where there is a known history of a genetic or other condition, site study teams will be encouraged to ensure that standard of care processes are not disrupted and that referrals are made to relevant specialists as appropriate.

Study teams will be asked to record locally any information on numbers of participants approached vs consented. We will receive aggregated data on consent numbers as a numerator of those approached in order to determine the uptake rate of the study.

# Pathway for recording consent post-partum

The Generation Study does not provide a formal post-partum consent pathway. However, we acknowledge the practicalities associated with conducting a witnessed consent close to birth and do allow for delayed recording of consent in the Generation Study Portal for mothers / birthing parents who deliver after having a verbal consent conversation antenatally (as detailed below).

This situation can arise, for example, when a mother / birthing parent has been advised to take time to reflect on the participation decision after a face to face discussion in late pregnancy, or when registering their interest for participation on the study website close to birth.

Parents should be made aware that participation may not be possible unless:

- 1. A consent conversation has been completed (to the extent that the 11 consent statements in the consent form have been discussed),
- 2. The birthing parent has been advised to take time to consider participation (acknowledging that this will vary person to person), and
- 3. The birthing parent has verbally expressed a willingness to participate. If an initial introduction to the study has been made but a consent conversation covering the main points in the consent form has not been completed by the time the baby is born (as outlined in the point above), the birthing parent would not be eligible to participate in the study. Potential participants should be made aware of this risk upfront.

Process

- A verbal expression of willingness to participate should be recorded in the patient notes to ensure visibility for the wider ward team and in line with usual expectation for clinical research interactions.
- If the baby is delivered whilst the potential participant (who has verbally expressed interest in participating see point above) is reflecting on their decision, a cord blood sample should still be taken. Ideally, verbal ratification from the participant at the time should be sought before sampling. Otherwise staff should follow-up as soon as reasonably possible with the birthing parent to affirm their choice to consent.
- The sample can be refrigerated as per standard protocol
- Consent should then be formally recorded in the Generation Study Portal. This should include the date that verbal consent was taken, not the date entered into GSP (if different). This should happen as soon after birth as possible, but no longer than 28 days post-partum. If written authorisation cannot be sought within this period, then the sample should be discarded per local policy and the person will not be considered as enrolled into the Generation Study.

If the cord blood sample is missed the heel prick pathway can be followed only after the mother/birthing parent's formal consent is recorded in the Generation Study Portal

# 8. Sample Collection

## Introduction

The Generation Study sampling strategy is based on the results of our feasibility study (see Section 4). This study demonstrated that cord blood was an ideal sample type. One sample of cord blood will be collected from each baby, this may take place in hospital, or at home if it is a home birth. NHS England encourages mothers/birthing parents to deliver at home where it is safe to do so. 161,162

In some cases, obtaining a cord blood sample may not be possible, for instance where there is an emergency c-section. However, it is important to facilitate the collection of a sample where it is safe for the baby. In these cases a heel prick sample may be taken or, if the baby is admitted, a sample may drawn from an indwelling line.

Importantly, the procurement of any sample other than cord blood is at the discretion of the research teams, in collaboration with clinical teams. Safety of the baby is paramount. Parents should be informed of the risks of sampling in advance, and verbal parental consent for a secondary sample (heel prick or blood from an indwelling line) should be sought. Secondary samples must be procured as close to birth as possible. If this is not possible, recruiting centres will be asked not to carry out heel prick sampling in the home context until after the Newborn Blood Spot test has been taken, to avoid the risk that parents might conflate the Generation Study sample with the Newborn Blood Spot standard of care.

**For sites:** Please refer to the separate study sampling guide for recruiting sites for details relating to sample collection, local processing and shipping. All NHS staff at recruiting sites handling study samples should adhere to the guidelines in this supporting document.

More detail on each sample type is provided below:

# Preferred sample - Cord Blood

- Can be obtained from babies born in hospital and those born at home.
- Should be collected by a trained member of research or clinical staff just after the birth, on Day 0.
- Approximately 3mls should be obtained by needle aspiration and placed in an EDTA tube.
- The sampling of cord blood poses no risk to the mother / birthing parent or the baby.

# Secondary sample - Heel Prick

- Can be obtained from babies born in hospital and those born at home, where it has not been possible to collect cord blood
- The sample should be taken as close to Day 0 as possible.
- Heel prick sampling will be at the discretion of sites and depending on capacity. Heel prick sampling must not take place on the same day as the Newborn Blood Spot test is carried out (usually day 5)
- Before a heel prick is taken, parents should be informed the cord blood has not been collected. The risks of the heel prick (mainly brief pain for the baby) should be explained.
- Parents should be invited to opt-out of a heel prick, however must be made aware that this would also constitute a withdrawal from the study as we will not have a sample to sequence.
- The blood may be collected into an EDTA capillary tube or an EDTA microtainer.
- The latest a sample can be taken AND registered is 28 days after birth. After 28 days the participant will be automatically withdrawn from the study if no sample has been registered and will be issued communication to reflect this, from Genomics England.

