# Baby born at a different hospital than planned

In cases where a consented participant delivers at a different hospital to their planned delivery hospital:

- If the delivery hospital is **not** participating in the study, the cord blood sample will not be taken. The hospital that originally consented the participant may invite the participant back to give a heel prick sample. If a heel prick sample is not obtained within study timelines the participant will be withdrawn or removed from the study.
- If the delivery hospital **is also** participating in the study, the delivery hospital must confirm consent by checking the Generation Study Portal, and/or checking with the hospital that

consented the participant. If consent is confirmed, the delivery hospital may take and dispatch the cord blood sample as normal.

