# Preparation for returning results

In preparation for the return of results:

- Parent information and contact details will be obtained when consent takes place. These details will be used to return results. Parents will be advised to keep their details updated with the Newborn Genome Programme.
- Any language or accessibility needs for will be noted. Additional support or resources needed to return results will be considered. This may include translation and interpretations of communications.
- NHS Spine will be used during the return of results process to check whether the baby and mother / birthing parent are alive. If the baby or mother / birthing parent have died, this will be flagged and results will be returned via a non-standard pathway.

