#### Mother / birthing parents or newborns who die

Both the mother / birthing parent (consenting individual) and the baby may be enrolled in the study and later die. The death of a mother/birthing parent, or of a child, will be managed as soon as the Newborns Genome Programme becomes aware of it, as follows:

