#### Ongoing participation of a baby / child following death of mother / birthing parent

If a mother / birthing parent of a baby in the Generation Study dies, the parental consent that had been provided for the child to participate in the Generation Study will no longer be legally valid. Consent must thus be obtained from another individual with legal parental responsibility for the child, as soon as practically possible. The precise pathway for making contact with another individual whom has parental responsibility will be determined on a case-by-case basis, sensitive and empathetic to the experience of the collective family unit. Obtaining a new consent may involve liaison with clinical teams or social workers at various times. Because the death of a mother / birthing parent invalidates the legality of the baby's participation in the |Generation Study, the data pertinent to the baby will not be further processed until consent has been provided by another individual with parental responsibility. If this consent is not provided, the baby will be fully withdrawn from the study. However, if the baby's genomic sequence is being processed by Genomics England at the time a mother / birthing parent dies, the study result will still be returned through the appropriate channels.

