#### Child

If a child in the Newborns Genome Programme dies, the same processes for the demise of a mother/birthing parent will be followed. The child will not automatically be withdrawn from the study, and the mother/birthing parent may be approached to ratify consent or withdraw the child at an appropriate time in the future. These situations would be dependent on input and clinical judgement, as to the manner to best navigate the continued participation of the child without causing harm to the grieving parents, and weighted with the benefit of the child's data remaining in the project for future research.

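### The day-28 no-sample withdrawal rule states no exception for deaths and, for a baby who dies unsampled, conflicts with the Section 17 rule on deceased children

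*Protocol*

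**What the plan says.** Section 8, Secondary sample - Heel Prick, sets the time limit: "The latest a sample can be taken AND registered is 28 days after birth". It then gives the consequence: "After 28 days the participant will be automatically withdrawn from the study if no sample has been registered and will be issued communication". The rule sits in the heel-prick subsection but is worded for any participant without a registered sample. The subsection on a baby born at a different hospital has a companion rule: "If a heel prick sample is not obtained within study timelines the participant will be withdrawn or removed from the study".

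Section 17, Child, deals with a participating child who dies: "The child will not automatically be withdrawn from the study, and the mother/birthing parent may be approached to ratify consent or withdraw the child". It leaves the timing and manner of contact to clinical judgement, so as not to harm grieving parents. The paragraph introducing the Section 17 rules says that a death "will be managed as soon as the Newborns Genome Programme becomes aware of it".

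For the baby of a mother who dies, Section 17 requires fresh consent from another person with parental responsibility and adds: "If this consent is not provided, the baby will be fully withdrawn from the study".

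The protocol's explicit check for deaths is in Section 11, Preparation for returning results: "NHS Spine will be used during the return of results process to check whether the baby and mother / birthing parent are alive".

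**The concern.** Consent is normally taken before birth and the sample after it. A baby can therefore be enrolled, be born, and die within four weeks without a sample having been registered. Section 8 and Section 17 then tell staff to do different things.

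Two things are at stake. The first is the family: an automatic withdrawal notice reaching newly bereaved parents is the kind of contact that Section 17 wants handled with judgement. The second is a modest measurement point. Section 13 (Process evaluation) and Appendix A (Acceptability) use withdrawal rates as evidence of how acceptable the programme is. A death processed as an automatic withdrawal would be counted there although it says nothing about acceptability.

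**Working it through.** No sample-size or event figure is involved, so the check is a comparison of the text.

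1. **Can the overlap occur?** Yes. Section 7 takes consent in pregnancy. Section 8 makes any sample other than cord blood discretionary, with the baby's safety first. Section 6 leaves sampling after complicated births or NICU admission to case-by-case decision. A baby who dies early may have no sample.

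2. **The two rules for that baby.**

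| | Section 8, heel prick | Section 17, Child |
|---|---|---|
| Trigger | No sample registered by day 28 | The child has died |
| Status | Withdrawn automatically | Not withdrawn automatically |
| Contact | Communication issued by the sponsor | Parent may be approached at a suitable later time, on clinical judgement |
| Exception stated | None for death | None for absence of a sample |

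Both triggers are met and the outcomes differ. Neither section cites the other. The companion rule for birth at a non-participating hospital also has no exception for death, although it does not call the withdrawal automatic.

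3. **Do the Section 11 safeguards clearly reach this case?** Not clearly. The Spine check is placed within the return of results. Section 11 counts failure to produce a result as one of its three result types, and the subsection on sample failure mentions the case where no sample was taken. That subsection, however, specifies a standard letter personalised only by name. The written routes for a death appear under the other two result types: no conditions suspected (regional coordinator, case by case) and condition(s) suspected (the subsection on a baby already deceased). None is written for the no-sample letter, and the day-28 notice in Section 8 does not refer to Section 11.

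4. **Does the awareness provision in Section 17 close the gap?** Only if the programme knows of the death. The day-28 step does not say that anyone looks first.

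5. **The mother's death.** Section 17 makes the baby's participation depend on new consent and ends in full withdrawal if consent is not given. The rule against automatic withdrawal of a deceased child does not govern this case. What is missing is any statement that the day-28 clock pauses while another person with parental responsibility is approached.

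6. **Effect on a reported measure.** Appendix A lists withdrawal rates, with reasons where possible. A withdrawal generated by the day-28 rule would naturally carry the reason that no sample was registered, so the death behind it could be lost.

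**The case against.** The strongest reply is that the two rules answer different questions. Section 17 says that death alone does not end participation, and part of its reason is the research value of the child's data. Section 8 withdraws because there is nothing to sequence, and a baby never sampled has no genome to keep. This narrows the conflict to one uncommon case, but it does not tell staff which instruction to follow there. The Section 17 wording on approaching grieving parents applies whether or not a sample exists.

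A second reply is that a check may well happen. Section 11 can be read as placing the no-sample letter under the Spine check. Sections 7 and 12 give the programme demographic updates after birth that do not depend on a sample. Section 17 also escalates unanticipated situations, and sites have separate operational guides. This stands as far as it goes. A reader might infer that the sponsor sends the notice without checking whether anyone has died. The protocol does not say that; it is silent on whether the check governs the day-28 step.

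A reader might also infer that a mother's death contradicts the rule on deceased children. It does not, because a different Section 17 provision covers it.

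**Conclusion.** The point holds in a limited form. For a baby who dies before day 28 with no registered sample, Section 8 and Section 17 give opposite instructions and the protocol does not say which prevails. For a mother who dies, the defect is an unstated interaction between the day-28 clock and the search for new consent.

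The size cannot be given. The protocol has no figure for deaths in the first 28 days or for deaths without a registered sample. It would be tempting to apply the feasibility study's 20% cord-collection failure to an assumed mortality rate. That 20% is failure of cord blood alone, before the heel-prick and indwelling-line alternatives, so it is not a rate of having no registered sample.

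Nor do the documents support a claim that the study's mortality results are affected. The mortality measure in Appendix A is restricted to apparent true positives, and a baby who was never sequenced cannot be one. The supported consequences are a possible automatic notice to bereaved parents and some deaths counted as withdrawals. The correction is worth making because it is cheap and the distress is avoidable.

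**What to change.** Reconcile the two withdrawal rules in Section 8 with the Section 11 text on preparing and returning results and with the Section 17 provisions on deaths. Specifically:

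- State in Section 8 that the NHS Spine check already used in Section 11 is run on baby and mother before the day-28 step.
- Where either has died, hold the automatic withdrawal and its communication and pass the case to the existing regional-coordinator route. Where the mother has died, say what happens to the day-28 limit while new consent is sought.
- Add the same cross-reference to the sample-failure subsection of Section 11, so that the standard letter is covered too.
- In the withdrawal rate used in the process evaluation and Appendix A, report deaths separately from withdrawals.

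The cost is a few sentences, a look-up in a system the protocol already uses, and one reporting category. No new data collection is needed.
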